## PROTOCOL SUMMARY

TITLE:	A Post-Market Study of Transcatheter Perivascular Renal Denervation for the Treatment of Hypertension using the Ablative Solutions Inc. Peregrine System™ Infusion Catheter
SHORT TITLE:	The Peregrine Post-Market Study
PROTOCOL ID:	CR0001
INVESTIGATIONAL PRODUCT:	Peregrine System™ Infusion Catheter
INDICATION:	Hypertension
ClinicalTrials.gov ID:	NCT02570113
PHASE:	Post market clinical follow up study
SPONSOR:	Ablative Solutions, Inc. [name]
COORDINATING INVESTIGATORS:	[name]. med. [name]
PROTOCOL VERSION:	Rev K
DATE:	16 April 2018

\*

INVESTIGATIONAL PRODUCT	
Name of Product	Peregrine System™ Infusion Catheter
CLINICAL CONDITION/INDICATION	
Hypertension	
Protocol ID	CR0001
Protocol Title	A Post-Market Study of Transcatheter Perivascular Renal Denervation for the Treatment of Hypertension using the Ablative Solutions Inc. Peregrine System™ Infusion Catheter
Short Title	The Peregrine Post-Market Study
Study Phase	Post market clinical follow up study
PLANNED STUDY PERIOD	
Initiation	November 2015
Study Completion	May 2019
Duration	Approximately 3.5 years
STUDY OBJECTIVES AND PURPOSE	
Study Purpose	To collect additional safety and performance data pertaining to renal denervation by using dehydrated alcohol as a chemical neurolytic agent delivered into the adventitial/peri-adventitial area of the renal arteries for the purpose of renal denervation, using the Peregrine Catheter, in patients with hypertension.
Objective	The objectives of this post-market study are to collect additional safety and performance data pertaining to renal denervation by using dehydrated alcohol as a chemical neurolytic agent delivered into the adventitial/peri-adventitial area of the renal arteries for the purpose of renal denervation, using the Peregrine Catheter, in patients with hypertension.
STUDY DESIGN	
Study Type/ Classification/ Discipline	Post market clinical follow up study for safety and performance (ambulatory blood pressure monitoring [ABPM], office blood pressure)
Study Indication Type	Treatment

Study Design	
This post-market study is a prospective, single arm, open label, multicenter trial. Up to 60 subjects with hypertension will be treated with 0.6 mL of dehydrated alcohol as the neurolytic agent per renal artery. The data of the first 5 treated subjects in the study (including renal duplex ultrasound) will be assessed at the 1-month follow-up by the Data Safety Monitoring Board (DSMB). If no safety concern arises, treatment with 0.6 mL of alcohol will continue according to the protocol.
 
Contenting subjects will be assessed for eligibility and baseline data collected. Subjects will attend the study site for the day of procedure. Subjects will be discharged from the study site per the physician's judgment. Subjects must be maintained on his/her baseline anti-hypertensive medications at the same doses through the 6 months follow up visit unless the study subject has symptomatic hypotension requiring anti-hypertensive medication reduction. Planned increases in anti-hypertensive medications must be in alignment with JNC-8 and/or European Hypertension Guidelines and with approval from the sponsor.
 
Follow-up visits will be performed at 7 days, 1 month, 3 months, 6 months and 12 months post-procedure.

Study Geography/ Number of Planned Investigational Sites	Europe: up to 10 sites in Europe.
Number of Groups/ Arms/ Cohorts	1 group
Number of Subjects	Up to 60
Planned Duration of Subject Participation	Up to 12 months
INVESTIGATIONAL PRODUCT	
Product	
Peregrine System™ Infusion Catheter used to deliver a neurolytic agent (such as dehydrated alcohol) to the perivascular area of the renal arteries to ablate the afferent and efferent sympathetic nerves serving the kidneys
 
Dose: 0.6 mL alcohol per treated renal artery.
 
Mode of administration: Direct infusion to the perivascular space, during an endovascular procedure

SUBJECT SELECTION	
Subjects will be enrolled in the study at the time they sign the informed consent form. No study-specific procedures will be performed until after the subject has provided written informed consent.	

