STATISTICAL ANALYSIS PLAN SUMMARY

TITLE: A Post-Market Study of Transcatheter Perivascular Renal Denervation for the Treatment of Hypertension using the Ablative Solutions Inc. Peregrine System™ Infusion Catheter

SHORT TITLE: The Peregrine Post-Market Study

PROTOCOL ID: CR0001

INVESTIGATIONAL PRODUCT: Peregrine System™ Infusion Catheter

INDICATION: Hypertension

ClinicalTrials.gov ID: NCT02570113

PHASE: Post market clinical follow up study

SPONSOR: Ablative Solutions, Inc.
[name]

COORDINATING INVESTIGATORS: [name]. med. [name]

SAP VERSION: Final 2.0

DATE: 28 October 2018

*

ENDPOINTS AND STATISTICAL ANALYSIS**Sample Size Calculation**

The study is not powered for formal hypothesis testing.

The primary safety endpoint is defined by the absence of any of the following events as adjudicated by the CEC through 1-month post procedure:

1. Peri-procedural major vascular complications
2. Major Bleeding as defined by the thrombolysis in myocardial infarction (TIMI) Bleeding Classification
3. Acute Kidney Injury (AKI) within 1 month of the procedure
4. Peri-procedural death (within 1 month of the procedure)

With a sample size of 60 evaluable subjects for the primary safety endpoint which is expected to vary between 85% and 100%, the associated width of the 95% 2-sided exact binomial confidence intervals range from 19.5% to 6.0%, respectively. This accuracy was deemed satisfactory and sufficient to fulfill the study objectives and to provide relevant information to design appropriately a larger study.

The primary performance endpoint is defined as a reduction of 24-hour mean ambulatory systolic blood pressure following treatment at 6 months, as compared to baseline. Assuming 10% of subjects will not participate in the performance evaluation at 6-months (death, drop-out, loss-to-follow-up, withdrawal), then with a sample size of 54 evaluable subjects and results on primary performance endpoint expected to vary between 85% and 100%, the associated width of the 95% 2-sided exact binomial confidence intervals range from 20.5% to 6.6%, respectively. This accuracy was deemed satisfactory and sufficient to fulfill the study objectives and to provide relevant information to design appropriately a larger study.

Endpoints and Planned Statistical Analysis

The following populations are defined for analysis:

- Full Analysis Set (FAS): The full analysis set contains all consented and treated subjects

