- Per-protocol (PP): The per-protocol analysis set consists of all subjects treated with the study dose (0.6 mL dehydrated alcohol) and with no major protocol deviations. If any subjects meet these criteria for removal from the full analysis set, then all endpoint analyses will be additionally conducted in this subset of subjects. These analyses will be considered supplementary

All analyses will be conducted using the FAS unless otherwise specified. The FAS will be the primary analysis set for all statistical analyses

Primary Safety Endpoint

The primary safety endpoint is defined as the absence of any of the following events as adjudicated by the Clinical Events Committee (CEC) through 1-month post procedure:

1. Peri-procedural major vascular complications
2. Major Bleeding as defined by the TIMI Bleeding Classification
3. Acute Kidney Injury (AKI) within 1 month of the procedure
4. Peri-procedural death (within 1 month of the procedure)

Primary Performance Endpoint

The primary performance endpoint is defined as any reduction of 24-hour mean ambulatory systolic blood pressure following treatment at 6 months, as compared to baseline.

Secondary Safety Endpoints

Secondary safety endpoints include:

1. Proportion of subjects with a decline in estimated glomerular filtration rate (eGFR) by >25% from baseline to 6-month follow-up;
2. Change in serum creatinine from baseline to 6-month follow-up
3. New renal arterial stenosis > 60% from the baseline at the 6-month follow-up, to be confirmed by the same imaging method used at baseline.
4. Stroke or transient ischemic attack (TIA) within 1 month of the procedure
5. Myocardial Infarction (MI) within 1 month of the procedure
6. Major Adverse Events (MAEs) through 6-month post-procedure.

Adverse events will be recorded at each of the follow-up periods. Severity, device relatedness, and sequelae of each adverse event will be recorded.

Secondary Performance Endpoints

Secondary performance endpoints include the following:

1. Changes in antihypertensive medications at 7 days, 1-, 3-, 6- and 12-months post-procedure
2. Changes in systolic and diastolic clinic/office blood pressure following treatment compared to baseline, assessed at 7 days, 1-, 3-, 6- and 12-months post-procedure

3. Changes in systolic and diastolic 24-hour mean daytime and nighttime ambulatory blood pressure, assessed at 1-, 3-, 6- and 12-months post-procedure

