- Unless otherwise noted, only complete data will be reported and no imputation for missing values will be conducted. Sensitivity analyses will be conducted for the primary safety and efficacy endpoints whereby missing data will be imputed using multiple imputation and LOCF methods.

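### A 6-month systolic fall that follows an antihypertensive increase counts as primary performance success, and no planned analysis is sure to separate it out

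*Protocol*

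**What the plan says.** **Medication rule (Protocol Summary, Study Design).** "Subjects must be maintained on his/her baseline anti-hypertensive medications at the same doses through the 6 months follow up visit". The one exception stated is a reduction for symptomatic hypotension. The next sentence reads "Planned increases in anti-hypertensive medications must be in alignment with JNC-8 and/or European Hypertension Guidelines and with approval from the sponsor" and does not say whether it applies before or only after month 6.

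**Primary performance endpoint (SAP).** Success is "any reduction of 24-hour mean ambulatory systolic blood pressure following treatment at 6 months", relative to baseline. Medication is not mentioned.

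**Analysis sets (SAP, Endpoints and Planned Statistical Analysis).** "The full analysis set contains all consented and treated subjects", and this set (FAS) is primary. The per-protocol (PP) set is "all subjects treated with the study dose (0.6 mL dehydrated alcohol) and with no major protocol deviations". If it differs from the FAS, "then all endpoint analyses will be additionally conducted in this subset of subjects", as supplementary results. The text provided does not define a major deviation.

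**Missing data (SAP, General Considerations).** "Sensitivity analyses will be conducted for the primary safety and efficacy endpoints whereby missing data will be imputed using multiple imputation and LOCF methods".

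**Medication reporting (SAP, Secondary Performance Endpoints, item 1).** "Changes in antihypertensive medications at 7 days, 1-, 3-, 6- and 12-months post-procedure" are listed as a separate endpoint.

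**Purpose (SAP, Sample Size Calculation and General Considerations).** There is no hypothesis testing and intervals are descriptive, but the results are meant to inform the design of a larger study.

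**The concern.** The dose-stability rule shows that the sponsor sees constant medication as a condition for interpreting the 6-month pressure. The analysis does not carry that condition through. Take a subject whose regimen is stepped up at month 2 and whose 24-hour systolic pressure is below baseline at month 6. That subject is a success, even if the added drug produced the fall.

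The study has one arm, so there is no control group in which similar escalation would show. Clinicians are also more likely to escalate subjects who are not responding, and those are the subjects whose classification can change. At stake is a somewhat high success proportion, and a somewhat large mean fall, carried into the planning of the next trial.

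**Working it through.** **Step 1. The plan's own figure.** The SAP gives exact 95% interval widths of 20.5% to 6.6% for 54 evaluable subjects at success rates of 85% to 100%. The 54 is 60 × 0.9. Clopper-Pearson gives 72.9% to 93.4% for 46/54 (width 20.5 points) and 93.4% to 100% for 54/54 (width 6.6 points). Both widths reproduce, so the issue is what is counted and not the arithmetic.

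**Step 2. Following one escalated subject through the plan.**

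| Planned analysis | Effect on a fall observed after an increase |
|---|---|
| Primary, FAS | Counted as success |
| Multiple imputation and LOCF | None, because the value is not missing |
| Supplementary PP | Removed only if the increase is a major deviation |
| Medication-change summaries | May show how many had an increase; not linked to each subject's pressure result |

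If the sentence on increases applies only after month 6, an earlier increase is a deviation, and PP may or may not remove it. If it applies earlier too, an approved increase may not be a deviation at all. The FAS result is the same on both readings.

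**Step 3. Size under an assumed model.** The 85% rate and n = 54 come from the SAP. The SD, escalation fraction and drug effect are assumptions.

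- Change without extra drug: D ~ Normal(μ, 15 mmHg) with P(D < 0) = 0.85, so μ = −1.0364 × 15 = −15.55 mmHg.
- Escalated fraction e = 10%; drug effect d = 5 to 10 mmHg.
- Subjects that effect d could convert (0 ≤ D < d): g(d) = P(D < d) − 0.85.
  - g(5) = Φ(20.55/15) − 0.85 = 6.46 points
  - g(10) = Φ(25.55/15) − 0.85 = 10.57 points

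| Who is escalated | Formula | d = 5 | d = 10 |
|---|---|---|---|
| Unrelated to response | e × g | 0.65 | 1.06 |
| Random sample of non-reducers | e × g / 0.15 | 4.3 | 7.0 |
| Maximum: non-reducers nearest zero change | min(e, g) | 6.5 | 10.0 |

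Entries are percentage points. One subject is 100/54 = 1.85 points, so the rows are under 1 subject, 2.3 to 3.8 subjects, and 3.5 to 5.4 subjects.

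**Step 4. Varying the assumptions.**

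- e = 5% to 15% at SD 15: unrelated 0.3 to 1.6; random non-reducers 2.2 to 10.6; maximum 5.0 at e = 5% and 6.5 to 10.6 at e = 15%. Only 15% are non-reducers, so the last two rows cannot use a larger e.
- SD 12 to 18 at e = 10%: unrelated 0.6 to 1.2; random non-reducers 3.7 to 7.9; maximum 5.6 to 10.0.
- Underlying rate 95%, SD 15, e = 10%: unrelated 0.3 to 0.4; maximum 2.6 to 4.0.
- Underlying rate 100%: no inflation, since nobody is left to convert.

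**Step 5. Scale.** Two conversions move 46/54 (85.2%, 72.9–93.4) to 48/54 (88.9%, 77.4–95.8). Four move it to 50/54 (92.6%, 82.1–97.9). The mean change shifts by e × d = 0.5 to 1.0 mmHg, against a 95% half-width of 1.96 × 15/√54 = 4.0 mmHg.

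**The case against.** The case for leaving the plan alone is substantial.

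- **Conduct already limits the problem.** Doses are to be held to month 6, and entry requires a stable regimen of at least three drugs. The most natural reading is that increases before month 6 are not allowed. A reader might infer that the protocol invites early escalation so as to lift the success rate. The documents do not support that: the sentence on increases sits beside a firm stability rule and may concern only later visits.
- **The plan is not silent.** It repeats every endpoint in a PP set and reports medication changes at each visit. A reader might infer that escalation goes unexamined, and that goes too far. What stands is that PP status depends on an undefined term and that medication counts are not tied to individual pressure results. A count caps the inflation of the proportion, but it does not show who was converted or how far the mean moved.
- **Analysing the observed value whatever medication followed is legitimate.** This stands, and it is why the primary analysis should not change.
- **The size rests on assumptions, and the shifts fit within the planned interval.** Both are true, but the interval describes sampling error and does not allow for bias. A reader might also take 4.3–7.0 points as a ceiling. It is one scenario; selective escalation of subjects close to zero change gives up to 6.5–10.0. Nor is that ceiling the likely case: if clinicians escalate those with the highest pressures, those subjects may be the hardest to convert.
- **Increases are only half the story.** The one change expressly allowed before month 6 is a reduction for symptomatic hypotension, which pushes the 6-month pressure up and can hide a true fall. This stands, and the remedy must cover both directions.

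Only summaries of the protocol and SAP are available, so fuller text may contain a rule that settles the point.

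**Conclusion.** The point holds as a minor one. In the text provided, a fall after an antihypertensive increase is a primary success in the FAS on either reading of the medication rule, and only the PP set might take it out.

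The size is unknown and probably modest. Under the base assumptions it runs from less than one subject in 54 when escalation is unrelated to response to at most 6.5–10.0 points under the most selective escalation, and it shrinks as the underlying rate approaches 100%. The documents supply no escalation rate, SD or drug effect.

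They do not support concluding that the primary result is invalid or that escalation will be common. Nor would resolving this point allow the fall to be attributed to denervation: regression to the mean and changes in adherence would remain.

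**What to change.** Keep the as-observed FAS result as primary. Add one pre-specified sensitivity analysis of the success proportion and of the mean 24-hour systolic change:

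1. Set ambulatory values after the first antihypertensive change to missing. A change is a drug added or stopped, or a dose raised or lowered.
2. Date the change by its recorded date, or otherwise by the first visit at which it is reported.
3. Apply the multiple imputation and LOCF already planned. The imputation model should include baseline and any 1- and 3-month ambulatory values taken before the change. LOCF carries the last value before the change; if there is none after the procedure, the change is zero and the subject counts as not reduced.
4. Show results for increases alone and for any change.
5. As a bound on the proportion only, score subjects with an increase before the 6-month ambulatory reading as non-responders.

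A line saying whether such an increase is a major deviation, and whether the sentence on increases applies before month 6, would help but does not replace the analysis.

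**Cost.** SAP wording, a derived flag and a few tables. The SAP already schedules medication changes and ambulatory pressure at 1, 3 and 6 months; whether exact change dates are recorded is not shown, hence rule 2.

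**Downsides.** The non-responder bound can only lower the rate: if 5 of 54 are escalated, by up to 5/54 = 9.3 points (46/54 = 85.2% to 41/54 = 75.9%). It also fails subjects whose pressure had already fallen. LOCF from baseline is harsh on a subject whose dose was cut early for hypotension. Dropping escalated subjects from PP may favour better responders. All of these results belong beside the primary one and should not replace it.

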### **Subject Inclusion Criteria**

Subjects must meet ALL of the following inclusion criteria to receive the percutaneous procedure:

1. Adult subject, age 18-80, male or female
2. Subject has a target treatment vasculature diameter of  $\geq 4$  mm and  $\leq 7$  mm and length of  $\geq 5$  mm
3. Subject has 3 measurements with a mean of office Systolic Blood Pressure of  $\geq 150$  mmHg AND office Diastolic Blood Pressure of  $\geq 85$  mmHg
4. Subject has a 24-hour mean systolic Ambulatory Blood Pressure Measurement (ABPM)  $\geq 135$  mm Hg with  $\geq 70\%$  valid readings (as determined by measurement device)
5. Subject with hypertension is receiving and adhering to a stable medication regimen of at least 3 anti-hypertensive medications of different classes (for at least 4 consecutive weeks), one of which must be a diuretic
6. Subject agrees to have all study procedures performed, to comply with medication regimen and is able and willing to comply with all study follow-up visits
7. Subject has provided written informed consent

### **Exclusion Criteria**

Any subject who meets ANY of the following exclusion criteria will not receive the percutaneous interventional procedure:

1. Subject has a contraindication known for conventional percutaneous interventional procedures such as:
  - intolerance for antiplatelet/anticoagulant therapy
  - known allergy to contrast media
  - bleeding disorders (such as bleeding diathesis, thrombocytopenia and severe anemia)
2. Subject has documented severe untreated obstructive sleep apnea (Apnea Hypopnea Index [AHI]  $\geq 30$  per hour)
3. Subjects with nephrotic syndrome
4. Subjects on immunosuppressive medications or immunosuppressive doses of steroids
5. Subject has type 1 diabetes mellitus
6. Subject is pregnant or nursing or planning to become pregnant
7. Subject has an estimated glomerular filtration rate (eGFR)  $\leq 20$  mL/min/1.73m^2, based on the Chronic Kidney Disease Epidemiology Collaboration (CKD-EPI) equation
8. Subject has imaging-assessed renal artery anatomy abnormalities or variations based on Investigator's evaluation of the screening images [i.e. magnetic resonance angiogram/angiography (MRA)/ computed tomography angiogram/angiography (CTA) examination and/or renal angiography]] meeting one of the following criteria:
  - Renal artery stenosis  $>60\%$  of the normal diameter segment (diameter stenosis, compared to the angiographically normal proximal or distal segment)

- Any renal artery abnormality or disease that, per the physician assessment, precludes the safe insertion of the guiding catheter (such as but not limited to severe renal artery aneurysm, excessive tortuosity, severe renal artery calcification)
- Previous renal angioplasty associated with stenting or other implants, that, per the physician's assessment, precludes the safe deployment of the Peregrine catheter components in the target treatment segment of the renal artery

9. Subject has a history of nephrectomy, a single kidney or kidney tumor, or urinary tract obstruction (with potential for hydronephrosis)
10. Subject is known to have a non-functioning kidney or unequal renal size (>2 cm difference in renal length between kidneys associated with a chronic kidney disease or a deterioration of the kidney function)
11. Subject has a renal transplant
12. Subject has a history of myocardial infarction, unstable angina pectoris, or stroke/transient ischemic attack (TIA) within the last six months from planned procedure
13. Subject has hemodynamically significant valvular heart disease
14. Subject has heart failure (New York Heart Association [NYHA] III or IV) or has an ejection fraction  $\leq 30\%$
15. Subject with chronic atrial fibrillation
16. Subjects who are allergic or intolerant of the neurolytic agent (such as dehydrated alcohol)
17. Any contraindication to the imaging as required per the protocol
18. Subject has a life expectancy of <12 months
19. Subject is currently enrolled in other potentially confounding research, i.e., another therapeutic or interventional research trial. Subjects enrolled in observational registries may still be eligible

STATISTICAL ANALYSIS PLAN SUMMARY

TITLE: A Post-Market Study of Transcatheter Perivascular Renal Denervation for the Treatment of Hypertension using the Ablative Solutions Inc. Peregrine System™ Infusion Catheter

SHORT TITLE: The Peregrine Post-Market Study

PROTOCOL ID: CR0001

INVESTIGATIONAL PRODUCT: Peregrine System™ Infusion Catheter

INDICATION: Hypertension

ClinicalTrials.gov ID: NCT02570113

PHASE: Post market clinical follow up study

SPONSOR: Ablative Solutions, Inc.
[name]

COORDINATING INVESTIGATORS: [name]. med. [name]

SAP VERSION: Final 2.0

DATE: 28 October 2018

*

ENDPOINTS AND STATISTICAL ANALYSIS**Sample Size Calculation**

The study is not powered for formal hypothesis testing.

The primary safety endpoint is defined by the absence of any of the following events as adjudicated by the CEC through 1-month post procedure:

1. Peri-procedural major vascular complications
2. Major Bleeding as defined by the thrombolysis in myocardial infarction (TIMI) Bleeding Classification
3. Acute Kidney Injury (AKI) within 1 month of the procedure
4. Peri-procedural death (within 1 month of the procedure)

With a sample size of 60 evaluable subjects for the primary safety endpoint which is expected to vary between 85% and 100%, the associated width of the 95% 2-sided exact binomial confidence intervals range from 19.5% to 6.0%, respectively. This accuracy was deemed satisfactory and sufficient to fulfill the study objectives and to provide relevant information to design appropriately a larger study.

The primary performance endpoint is defined as a reduction of 24-hour mean ambulatory systolic blood pressure following treatment at 6 months, as compared to baseline. Assuming 10% of subjects will not participate in the performance evaluation at 6-months (death, drop-out, loss-to-follow-up, withdrawal), then with a sample size of 54 evaluable subjects and results on primary performance endpoint expected to vary between 85% and 100%, the associated width of the 95% 2-sided exact binomial confidence intervals range from 20.5% to 6.6%, respectively. This accuracy was deemed satisfactory and sufficient to fulfill the study objectives and to provide relevant information to design appropriately a larger study.

Endpoints and Planned Statistical Analysis

The following populations are defined for analysis:

- Full Analysis Set (FAS): The full analysis set contains all consented and treated subjects
- Per-protocol (PP): The per-protocol analysis set consists of all subjects treated with the study dose (0.6 mL dehydrated alcohol) and with no major protocol deviations. If any subjects meet these criteria for removal from the full analysis set, then all endpoint analyses will be additionally conducted in this subset of subjects. These analyses will be considered supplementary

All analyses will be conducted using the FAS unless otherwise specified. The FAS will be the primary analysis set for all statistical analyses

Primary Safety Endpoint

The primary safety endpoint is defined as the absence of any of the following events as adjudicated by the Clinical Events Committee (CEC) through 1-month post procedure:

1. Peri-procedural major vascular complications
2. Major Bleeding as defined by the TIMI Bleeding Classification
3. Acute Kidney Injury (AKI) within 1 month of the procedure
4. Peri-procedural death (within 1 month of the procedure)

Primary Performance Endpoint

The primary performance endpoint is defined as any reduction of 24-hour mean ambulatory systolic blood pressure following treatment at 6 months, as compared to baseline.

Secondary Safety Endpoints

Secondary safety endpoints include:

1. Proportion of subjects with a decline in estimated glomerular filtration rate (eGFR) by >25% from baseline to 6-month follow-up;
2. Change in serum creatinine from baseline to 6-month follow-up
3. New renal arterial stenosis > 60% from the baseline at the 6-month follow-up, to be confirmed by the same imaging method used at baseline.
4. Stroke or transient ischemic attack (TIA) within 1 month of the procedure
5. Myocardial Infarction (MI) within 1 month of the procedure
6. Major Adverse Events (MAEs) through 6-month post-procedure.

Adverse events will be recorded at each of the follow-up periods. Severity, device relatedness, and sequelae of each adverse event will be recorded.

Secondary Performance Endpoints

Secondary performance endpoints include the following:

1. Changes in antihypertensive medications at 7 days, 1-, 3-, 6- and 12-months post-procedure
2. Changes in systolic and diastolic clinic/office blood pressure following treatment compared to baseline, assessed at 7 days, 1-, 3-, 6- and 12-months post-procedure

3. Changes in systolic and diastolic 24-hour mean daytime and nighttime ambulatory blood pressure, assessed at 1-, 3-, 6- and 12-months post-procedure
4. Changes in systolic 24-hour mean ambulatory blood pressure assessed at 1-, 3- and 12-months post-procedure
5. Changes in diastolic 24-hour mean ambulatory blood pressure assessed at 1-, 3-, 6- and 12-months post-procedure
6. Change in eGFR from baseline, to evaluate the progression of Chronic Kidney Disease (CKD) after 1, 3, 6 and 12 months
7. The progression of kidney disease in subjects with ≤ 60 mL/min/1.73m² will be evaluated by comparing the change in eGFR during the study to the historical loss (reduction) of eGFR during the 3 years prior to renal denervation for each individual subject
8. Change in albuminuria from baseline to 3 months post-procedure, with additional assessments at each study time point
9. Change in albuminuria categorization from baseline to 3 months post-procedure, with additional assessments at each study time point
10. Change in serum creatinine and cystatin-C from baseline to 3 months post-procedure, with additional assessments at each study time point

General Considerations

- Continuous variables will be summarized using standard quantitative statistics: number of non-missing observations, mean, standard deviation, median, quartiles and range (minimum and maximum observed values). The number of missing observations, if any, will also be summarized. Categorical variables will be summarized using classical frequency statistics: number of non-missing observations and percentages by categories. Number and percent of missing data, if any, will also be summarized.
- For all success/failure endpoints (including but not limited to primary safety endpoint), the 95% 2-sided exact binomial confidence intervals will be presented.
- Demographics, medical history and procedural characteristics will be summarized as noted above.
- For each variable, the baseline value will be defined as the last value collected before the procedure.
- There will be no formal hypothesis testing conducted in the study. Ninety-five percent confidence intervals, when presented, are intended to be descriptive in nature only. For binary variables, confidence intervals will be calculated via exact binomial methods. For continuous variables, the confidence interval of the mean will be constructed using the normal approximation.
- Unless otherwise noted, only complete data will be reported and no imputation for missing values will be conducted. Sensitivity analyses will be conducted for the primary safety and efficacy endpoints whereby missing data will be imputed using multiple imputation and LOCF methods.

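### The primary performance endpoint counts any fall in 24-hour systolic pressure as success, yet about half of subjects or more would meet it with no treatment effect, and the SAP sets no reference rate

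*SAP*

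**What the plan says.** The SAP (Primary Performance Endpoint) defines success as "any reduction of 24-hour mean ambulatory systolic blood pressure following treatment at 6 months, as compared to baseline". No minimum fall is set. Under Sample Size Calculation the endpoint is handled as a proportion: 54 evaluable subjects, an expected result between 85% and 100%, and exact 95% interval widths of 20.5% and 6.6%. That section also says the results should help to design a larger study.

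The Protocol Summary describes the design: "This post-market study is a prospective, single arm, open label, multicenter trial". Inclusion criterion 4 requires a 24-hour mean systolic pressure of at least 135 mmHg, so selection is on the endpoint variable, with a lower limit only.

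On baseline, the SAP (General Considerations) says "the baseline value will be defined as the last value collected before the procedure". The Protocol (Study Design) says that "subjects will be assessed for eligibility and baseline data collected", in one sentence. Neither document, as supplied, says whether a second ambulatory recording is made after the qualifying one.

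The SAP also says "There will be no formal hypothesis testing conducted in the study" and calls its intervals descriptive. It gives no performance goal, comparator or no-effect rate. Secondary performance endpoint 4 lists the change in systolic 24-hour mean at 1, 3 and 12 months, but not at 6.

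**The concern.** A success threshold of zero mmHg has a no-effect rate far from zero. Two recordings of an unchanged pressure differ by chance, and the second is lower about half the time. If subjects were chosen because the first recording was high, and that recording is also the baseline, regression to the mean pushes the rate above half.

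With no control arm and no stated reference, nothing in the SAP tells the reader what value the proportion and its interval should be set against. At stake is the interpretation of the only listed 24-hour mean systolic measure at 6 months, and the effect assumption carried into a later study.

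**Working it through.** **1. The plan's own figures.** The exact limits are the 0.025 quantile of Beta(x, n−x+1) and the 0.975 quantile of Beta(x+1, n−x). With n = 54 (60 × 0.9):

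- 46/54 (85.2%): 72.9% to 93.4%, width 20.5 points.
- 54/54: 93.4% to 100%, width 6.6 points.

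Both stated widths reproduce. The precision statement is correct for its inputs.

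**2. No-effect rate with a separate baseline recording.** Let each recording equal the subject's true value plus independent noise with within-subject SD σw. If the baseline is a fresh recording and nothing changes, the difference has mean zero and SD σw√2, so P(fall > 0) = 50% whatever σw is. This step needs no assumed SD.

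**3. No-effect rate if the qualifying recording is the baseline.** The documents give no mean or SD for 24-hour systolic pressure, so these inputs are assumptions: mean μ of 140, 145 or 150; between-subject SD σb of 10 or 13; σw of 6, 8 or 10 mmHg. Model: Y1 = T + e1 and Y2 = T + e2, with T ~ N(μ, σb²), zero effect, and Y1 ≥ 135 required. The proportions come from simulation with 2 million draws per cell. The mean spurious fall has a closed form:

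σw²/s × φ(α)/[1 − Φ(α)], with s = √(σb² + σw²) and α = (135 − μ)/s.

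For μ = 145, σb = 13, σw = 8: s = √(169 + 64) = 15.26; α = −10/15.26 = −0.655; fall = (64/15.26) × (0.322/0.744) = 1.8 mmHg.

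| μ, σb, σw | Any fall | Fall ≥5 | Fall ≥10 | Mean fall (mmHg) |
|---|---|---|---|---|
| 150, 10, 6 (lowest) | 52.8% | 30% | 13% | 0.6 |
| 145, 13, 8 | 56.5% | 38% | 23% | 1.8 |
| 140, 10, 10 (highest) | 62.2% | 47% | 33% | 4.15 |

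Over all 18 combinations the any-fall rate is 53–62%. On a wider grid (mean 135–160, σb 10–15, σw 6–12) it is 50.5–68.2%.

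**4. Non-specific change.** Adding an assumed average shift of −2 to −5 mmHg that is not due to the device moves three example cells from 54–61% to 61–75%. So 62% is not a ceiling.

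**5. What observed results would show (n = 54).**

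| Successes | Exact 95% CI | Excludes 50%? | Excludes 62%? |
|---|---|---|---|
| 29 (54%) | 39.6–67.4% | no | no |
| 35 (65%) | 50.6–77.3% | yes | no |
| 40 (74%) | 60.3–85.0% | yes | no |
| 41 (76%) | 62.4–86.5% | yes | yes |
| 46 (85%) | 72.9–93.4% | yes | yes |

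The chance of 46 or more successes is about 0.0002 if the no-effect rate is 62%, and 0.008 if it is 70%.

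**6. The 5 and 10 mmHg thresholds.** With a separate baseline, P(fall ≥ c) = 1 − Φ(c/(σw√2)). For σw = 6 to 10 this is 28–36% at 5 mmHg and 12–24% at 10 mmHg. These are lower than 50% but not zero.

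**The case against.** The strongest defence is that the SAP limits its own claims. The study is a post-market follow-up, runs no hypothesis test and treats its intervals as descriptive. A single arm is an accepted design for that purpose. If the result falls where the sponsor expects, at 85% or more, the lower limit of 72.9% clears every no-effect rate in step 3. All of that stands. It limits the problem to interpretation and to results below the planned range. It does not supply a reference value for the reader, and with no test or control the proportion and its interval are the whole primary performance result.

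Four stronger readings are tempting, and the documents do not support them.

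- A reader might take 53–62% as the no-effect rate of this trial. It depends on SDs that the documents do not give, and the model leaves out the office-pressure entry criterion.
- A reader might infer that the qualifying recording is the baseline. The last-value rule and the single sentence on eligibility and baseline point that way, but a repeat recording before the procedure is not ruled out. With one, the rate returns to about 50%.
- A reader might say that an inert procedure would give a majority with a tight interval. At 53–62% the exact interval is about 27–28 points wide, and at 29/54 it includes 50%.
- A reader might conclude that the 6-month change in size is not reported at all. Daytime and nighttime ambulatory changes and office pressure are listed at 6 months. Only the 24-hour mean systolic change is missing from the list.

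**Conclusion.** The concern holds as one of interpretation. The any-fall proportion has a no-effect rate of at least about 50%, and the SAP does not say so. This part rests only on the zero threshold and symmetric measurement noise.

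The excess over 50% is conditional on the qualifying recording being the baseline and on assumed inputs: 53–62% on the central set, about 50–68% on the wider set, and more if non-specific effects or medication increases lower pressure. The mean 6-month change would carry the same bias, about 0.6 to 4.15 mmHg on the central set.

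The practical consequence lies between 35 and 40 successes of 54, where the interval excludes 50% but not 62%. At the expected 46 of 54 the result would stand clear of the step 3 ranges, though not of the 75% reached with the largest non-specific shift tried. The sample-size precision figures are correct.

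**What to change.** In the SAP:

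1. State that the any-fall proportion and its exact interval are read against a no-effect rate of at least 50%, not against zero. State which pre-procedure ambulatory recording is the baseline. Do not write 53–62% in as a fixed benchmark.
2. Report beside it the proportions with falls of at least 5 and at least 10 mmHg, noting that each also has a non-zero no-effect rate.
3. List the mean 6-month change in 24-hour systolic pressure with its 95% interval, with a caveat that regression to the mean may contribute.
4. Label any model-based correction for regression to the mean as a sensitivity analysis only. The within-subject SD would have to come from post-procedure recordings, where noise is mixed with treatment effect and medication changes.

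The cost is SAP wording and a few extra tables from recordings already planned, with no added subjects or visits. The drawback is a less favourable headline and slightly more analysis work.
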